#### 4.4.2.2. Other Safety Endpoints

For other safety measures, the details are provided in Section 4.6.

#### 4.4.2.3. Patient-Reported Outcome

The analyses for patient-reported outcomes will be based on the EAS2 data.

#### 4.4.2.3.1. Treatment-Related Impact Measure – Diabetes (TRIM-D)

The TRIM-D is a self-administered instrument, which assesses the impact of diabetes treatment on participants' functioning and well-being across available diabetes treatments (Brod et al. 2009). The TRIM-D consists of 28 items each assessed on a 5-point scale, where higher scores indicate a better health state, with a recall period of "over the past 2 weeks." In addition to an overall score, the TRIM-D items assess 5 domains of impact:

- Treatment Burden (6 items: Question 1a, Question 2a to 2e)
- Daily Life (5 items: Question 3a to 3b, Question 5a to 5c)
- Diabetes Management (5 items: Question 4a to 4e)
- Compliance (4 items: Question 6a, b, c, e)
- Psychological Health (8 items: Question 6d, Question 7a to 7g)

Items within each domain are summed to obtain a raw domain score, which is then transformed to a scale of 0 to 100 to obtain a transformed domain score. The transformed domain score can be calculated by

$$\frac{(\text{sum of raw score - sum of lowest possible raw score})}{(\text{sum of highest possible raw score - sum of lowest possible raw score})} \times 100$$

For an example, Diabetes Management =  $((\text{sum of raw score -5})/(25-5))\times 100$ . If answer for the 5 questions in Diabetes Management (Question 4a to 4e) are all 1, then the sum of raw score is 5 and the transformed domain score is 0. All items can also be summed and transformed to obtain a transformed total score in a similar way.

Summary statistics for the transformed scores of each domain will be provided by study treatment. The scores at scheduled visits and the change from baseline will be analyzed by the MMRM model similar to the other efficacy endpoints (see Section 4.4.2.1). The last non-missing postbaseline observations will be analyzed by an ANCOVA model using treatment, strata (country, GLP-1 RA treatment at randomization, and baseline HbA1c stratum), and the baseline value of the dependent variable as independent variables.

In addition, sensitivity analysis will be conducted using the last non-missing postbaseline observations prior to or at the time of switch to LY3209590 with a prefilled pen to compare the patient-reported outcomes between LY3209590 with autoinjector and insulin glargine. The same ANCOVA model mentioned above will be used for the sensitivity analysis.

# 4.4.2.3.2. Diabetes Treatment Satisfaction Questionnaire – Status Version (DTSQ-s) Description of DTSQ-s

The DTSQ-s (Bradley and Lewis 1990; Bradley 1999) is a diabetes-specific, patient-reported outcome instrument that assesses the overall treatment satisfaction and perceived frequency of hyperglycemia and hypoglycemia. It is appropriate for use in both T1D and T2D. The DTSQ-s consists of 8 items that assess treatment satisfaction as well as concerns about hyperglycemia and hypoglycemia over the past few weeks, prior to the visit. Each item is rated on a 7-point Likert scale. Items 1, 4, 5 through 7, and 8 are rated from 0 (very dissatisfied) to 6 (very satisfied) and

can be summed up to produce a treatment satisfaction score. Items 2 and 3 evaluate the perceived frequency of hyperglycemia and hypoglycemia and are rated from 0 (none of the time) to 6 (most of the time).

Summary statistics for overall treatment satisfaction score, perceived frequency of hyperglycemia score, and perceived frequency of hypoglycemia score collected in DTSQ-s at baseline will be provided by study treatment. Treatment comparison will be conducted by Wilcoxon rank sum test.

# 4.4.2.3.3. Diabetes Treatment Satisfaction Questionnaire – Change Version (DTSQ-c) Description of DTSQ-c

The DTSQ-c (Bradley 1999) was designed to overcome potential ceiling effects in the status version. The DTSQ-c has the same 8 items as the status version but is reworded slightly to measure the change in treatment satisfaction rather than absolute treatment satisfaction. Each item is scored on a scale of -3 to +3. For Items 2 and 3, representing perceived frequency of hyperglycemia, and perceived frequency of hypoglycemia, the lower the score represents better the perception. For the remaining items:

- the higher the score represents the greater the improvement in treatment satisfaction
- the lower the score represents the greater the deterioration in treatment satisfaction, and
- a score of 0 represents no change.

Summary statistics for overall treatment satisfaction score, perceived frequency of hyperglycemia score, and perceived frequency of hypoglycemia score collected in DTSQ-c at postbaseline visits will be provided by study treatment. Wilcoxon rank-sum test will be used for treatment comparison. In addition, the last non-missing postbaseline observations prior to or at the time of switch to LY3209590 with a prefilled pen will be summarized and compared to the last non-missing postbaseline observations for insulin glargine by Wilcoxon rank sum test.

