# 4. Statistical Analyses

#### 4.1. General Considerations

Statistical analysis of this study will be the responsibility of Eli Lilly and Company (Lilly) or its designees. Any change to the data analysis methods described in the protocol will require an amendment ONLY if it changes a principal feature of the protocol. Any other changes to the data analysis methods described in the protocol, and the justification for making the change, will be described in the SAP or the final clinical study report. Additional exploratory analyses of data will be conducted as deemed appropriate.

Unless otherwise stated, the efficacy analyses will be conducted on either EAS1 or EAS2. Primary and key secondary (gated) objectives will be based on both treatment regimen estimand and efficacy estimand, while the other secondary and tertiary efficacy measures will be based on efficacy estimand. For treatment regimen estimand, EAS1 (see the definition in Section 3) will be used for analysis. For efficacy estimand, other secondary and tertiary efficacy measures, EAS2 (see the definition in Section 3) will be used for analysis.

Unless otherwise noted, the safety analyses will be conducted on the SS. Percentages will be calculated using the mITT population as the denominator. For events that are sex-specific, the denominator and computation of the percentage will include only participants from the given sex.

All tests of treatment effects will be conducted at a 2-sided alpha level of 0.05 and 2-sided 95% CIs will be calculated.

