## 5. Sample Size Determination

Approximately 670 participants will be randomly assigned to LY3209590 and insulin glargine in a 1:1 ratio.

With the assumption of 15% dropout at Week 52 (Visit 33), approximately 284 participants on LY3209590 and 284 participants on insulin glargine will complete 52 weeks of treatment.

The number of completers will provide at least 99% statistical power to show noninferiority between LY3209590 and insulin glargine using the upper limit of a 2-sided 95% CI and these assumptions:

- NIM of 0.4%
- no true difference between treatment groups, and
- an SD of 1.1%.

This sample size has at least 90% statistical power to show noninferiority between LY3209590 and insulin glargine using a 0.3% NIM at Week 52 (Visit 33).

The number of completers will provide 90% statistical power to show superiority between LY3209590 and insulin glargine for change in HbA1c from baseline to Week 52 (Visit 33), assuming an SD of 1.1% and true mean difference of -0.3%, and alpha of 0.05.

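### The DTSQ-c satisfaction score gets only an unadjusted Wilcoxon test, with no specified effect estimate or interval, unlike the SAP's other summed secondary questionnaire scores

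*SAP*

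**What the plan says.** The objectives tables in the protocol (Section 3) and the SAP (Section 1.1) list DTSQ change to Weeks 26 and 52 among the other secondary endpoints. The schedule of activities collects the status version, DTSQ-s, at Visit 3 only; the change version, DTSQ-c, is collected after baseline.

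- **DTSQ-s (SAP 4.4.2.3.2).** Summary statistics for satisfaction and for perceived hyperglycemia and hypoglycemia "collected in DTSQ-s at baseline will be provided by study treatment", and the arms are compared at baseline by a Wilcoxon test. No other use is planned.
- **DTSQ-c (SAP 4.4.2.3.3).** "Each item is scored on a scale of -3 to +3". The three scores are summarised at the postbaseline visits, and a "Wilcoxon rank-sum test will be used for treatment comparison". No covariate, stratum, effect estimate or interval is named.
- **TRIM-D (SAP 4.4.2.3.1).** The transformed scores get an MMRM, and an ANCOVA with treatment, country, GLP-1 RA use, baseline HbA1c stratum "and the baseline value of the dependent variable as independent variables".
- **DID-EQ Device Characteristics subscale (SAP 4.4.2.3.5).** MMRM and ANCOVA with the same strata; the instrument has no baseline.
- **Single-item responses.** The two SIM-Q questions, the DID-EQ global items and the Basal Insulin Experience item get Wilcoxon tests.
- **General rules (SAP 4.1).** Continuous outcomes are to be analysed by MMRM or ANCOVA, showing LS mean differences with intervals. "All tests of treatment effects will be conducted at a 2-sided alpha level of 0.05 and 2-sided 95% CIs will be calculated".

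**The concern.** The SAP follows a visible pattern: summed questionnaire scores are modelled with the strata, and single ordinal items are compared by rank tests. The DTSQ-c satisfaction score is a sum but is handled like a single item, and no reason is given.

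Two things are at stake. As written, the DTSQ-c section yields a p-value and descriptive summaries, but no specified treatment difference with an interval, although Section 4.1 promises intervals for tests of treatment effects. In addition, a satisfaction score measured before the first dose, and factors already used to stratify randomisation, are left out of the comparison. If they predict DTSQ-c, adjustment would sharpen the estimate and remove chance imbalance in those variables at no cost in data.

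**Working it through.** **The plan's own figures.** SAP Section 5 gives the sample size: "Approximately 670 participants will be randomly assigned to LY3209590 and insulin glargine in a 1:1 ratio". At 15% dropout it counts on 284 completers per arm. The superiority calculation for HbA1c is made "assuming an SD of 1.1% and true mean difference of -0.3%, and alpha of 0.05". With power = Φ(δ / (σ√(2/n)) − 1.96):

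- σ√(2/n) = 1.1 × √(2/284) = 0.0923.
- δ = 0.3: 0.3/0.0923 = 3.25, so power = Φ(1.29) = 90.1% (stated 90%, for superiority and for the 0.3% margin).
- δ = 0.4: 0.4/0.0923 = 4.33, so power = Φ(2.37) = 99.1% (stated at least 99%).
- Completers: 335 × 0.85 = 284.75 per arm.

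These reproduce. The documents give no SD, effect size or power for DTSQ-c.

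**The score.** SAP 4.4.2.3.2 forms satisfaction from items 1, 4, 5 to 7 and 8, which is six items. At -3 to +3 each, the DTSQ-c sum runs from -18 to +18. Items 2 and 3 are single 7-point scores.

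**Cost of not adjusting.** *Assumption:* a standardised effect d at which an unadjusted t-test with 284 per arm has 90% power, so d = (1.960 + 1.282) × √(2/284) = 0.272. For an 80% reference, d = 0.235.

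- Wilcoxon, normal shift: the effective sample size is n × 3/π = 0.955n.
- ANCOVA: the residual SD is √(1 − R²), where R² is the share of DTSQ-c variance explained jointly by the covariates. *Assumed range:* 0 to 0.30, because the documents give no correlation between DTSQ-s and DTSQ-c.

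For example, at the 90% reference the Wilcoxon power is Φ(3.242 × √0.955 − 1.96) = 88.6%. ANCOVA at R² = 0.10 has Φ(3.242/√0.90 − 1.96) = 92.7%.

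| R² | ANCOVA, 90% reference | Gain over Wilcoxon (88.6%) | ANCOVA, 80% reference | Gain over Wilcoxon (78.2%) |
|---|---|---|---|---|
| 0 | 90.0% | 1.4 | 80.0% | 1.8 |
| 0.05 | 91.4% | 2.8 | 82.0% | 3.8 |
| 0.10 | 92.7% | 4.1 | 84.0% | 5.8 |
| 0.20 | 95.2% | 6.6 | 87.9% | 9.7 |
| 0.30 | 97.2% | 8.6 | 91.8% | 13.6 |

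**Check by simulation.** There were 4,000 trials per cell, with 284 per arm and d = 0.272. The score was rounded and bounded at -18 and +18, with one prognostic covariate. Two shapes were used: symmetric (centre 0, SD 5) and piled up at the ceiling (centre 12, SD 7 before bounding). R² is on the scale before rounding and bounding.

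| R² | Symmetric: Wilcoxon / ANCOVA | Ceiling: Wilcoxon / ANCOVA |
|---|---|---|
| 0 | 89.2% / 90.3% | 87.3% / 86.6% |
| 0.10 | 88.1% / 92.6% | 86.9% / 89.7% |
| 0.30 | 87.9% / 97.1% | 86.6% / 95.0% |

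The Monte Carlo standard error of each figure is about √(0.87 × 0.13/4000) = 0.5 points. The 0.7-point advantage of Wilcoxon in the ceiling case at R² = 0 is therefore close to no difference. The gain from the strata alone was not computed.

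**The case against.** The strongest defence is that Wilcoxon is valid under randomisation and suits a bounded, possibly skewed score. That stands. So does the point that little rests on it: type I error control covers only the primary and key secondary HbA1c objectives, and no power is claimed for DTSQ.

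The TRIM-D comparison is also imperfect. TRIM-D is adjusted for its own baseline; DTSQ-c has none, and DTSQ-s is a different version scored 0 to 6 per item. The SAP adds that DTSQ-c was designed to overcome ceiling effects in the status version, so the link between starting level and rated change may be weaker than one would guess. This limits how confidently DTSQ-s can be called prognostic. It does not explain why the strata are left out, since the DID-EQ subscale is adjusted for them without any baseline.

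The missing interval does not by itself require ANCOVA: a rank-based shift estimate with its interval would meet Section 4.1. That is true, but it would still leave the baseline and strata unused.

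A reader might infer that the plan gives away power for nothing, or that linear models should extend to items 2 and 3. The documents support neither. They give no correlation, and Wilcoxon buys robustness. Items 2 and 3 are single 7-point responses, for which the SAP consistently uses rank tests. Nor would adjustment address reporting bias in an open-label trial.

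**Conclusion.** The point holds for the satisfaction sum. It is the one summed secondary questionnaire score compared without covariates and without a specified estimate or interval, against the SAP's own general rule and its handling of TRIM-D and the DID-EQ subscale. This is a gap in specification and probably in precision; it is not an invalid test.

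The size cannot be fixed from the documents. Over an assumed R² of 0 to 0.30 the power cost is about 1 to 9 points at a 90% reference and about 2 to 14 at an 80% reference. It disappears or reverses slightly if the covariates predict nothing and scores pile up at the ceiling. These figures rest on a constant shift, 284 completers per arm and assumed effect sizes. The missing estimate and interval do not depend on any of these assumptions and are the firmer part of the point.

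**What to change.** Before unblinding, amend SAP 4.4.2.3.3 as follows.

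- **Satisfaction sum, main analysis at Weeks 26 and 52:** an MMRM or ANCOVA of the TRIM-D type with treatment, country, GLP-1 RA use at randomisation, baseline HbA1c stratum and the baseline DTSQ-s satisfaction score. Report the adjusted difference with its 95% CI.
- **Satisfaction sum, sensitivity analysis:** keep the Wilcoxon test.
- **Items 2 and 3:** keep Wilcoxon as the main test.

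The cost is a few lines of SAP text and one more model, with no new data. The small downside is reliance on a linear model for a bounded score, which the retained rank test checks. If treatment codes have already been opened, the adjusted analysis can still be reported but should be labelled post hoc.

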#### 4.4.2.3.4. Simplicity Questionnaire (SIM-Q) Single Medication Status Version

The SIM-Q is a brief 10-item measure developed to assess the simplicity and complexity of treatment for T2D. This version of the instrument assesses the simplicity and complexity of a single medication. This measure asks participants to consider only the assigned study intervention when completing each item on a 5-point scale ranging from "Very complex" to "Very simple." In Study BDCW, only the last 2 questions of the SIM-Q will be completed – "How simple or complex is your medication treatment for diabetes?" and "Overall, how simple or complex is it to manage your diabetes, including medication, checking your blood glucose levels, diet, and any other aspects of diabetes treatment?"

The frequency and proportion of the response at Week 26 (Visit 25) and Week 52 (Visit 33) for each question will be summarized by study treatment. Treatment comparison will be conducted by Wilcoxon rank sum test. In addition, the last non-missing postbaseline observations prior to or at the time of switch to LY3209590 with a prefilled pen will be summarized and compared to the last non-missing postbaseline observations for insulin glargine by Wilcoxon rank sum test.

# 4.4.2.3.5. Diabetes Injection Device Experience Questionnaire (DID-EQ) Version 1.0 Description of DID-EQ

The DID-EQ (Matza et al. 2018) is a self-administered, 10-item questionnaire designed to assess participants' perceptions of non-insulin diabetes injection delivery systems for T2D. Each item is rated on a 4-point scale with higher scores indicating more positive perceptions of the injection device. Items 1 to 7 focus on specific characteristics of non-insulin injection device, and these 7 items comprise the Device Characteristics subscale. To compute the Device Characteristics subscale score, the seven individual item scores are first summed, resulting in a subscale raw score and then transformed to a scale with the possible range from 0 to 100 using the same calculation method in Section 4.4.2.3.1.

In addition, there are 3 global items:

- Item 8 assessing overall satisfaction
- Item 9 ease of use, and
- Item 10 convenience of non-insulin injection devices.

These 3 global items are each scored separately.

Summary statistics for the Device Characteristics subscale will be provided by study treatment. The scores at scheduled visits will be analyzed by the MMRM model with treatment, strata (country, GLP-1 RA treatment at randomization, and baseline HbA1c stratum [<8.0%, ≥8.0%]), visit and treatment-by-visit interaction as fixed effects. The last non-missing postbaseline observations will be analyzed by an ANCOVA model using treatment, strata (country, GLP-1 RA treatment at randomization, and baseline HbA1c stratum) as independent variables. In addition, sensitivity analysis will be conducted using the last non-missing postbaseline observations prior to or at the time of switch to LY3209590 with a prefilled pen to compare the patient-reported outcomes between LY3209590 with autoinjector and insulin glargine. The same ANCOVA model mentioned above will be used for the sensitivity analysis.

The frequency and proportion of the 3 global items at Week 26 (Visit 25) and Week 52 (Visit 33) will be summarized by study treatment. Wilcoxon rank sum test will be used for treatment comparison. In addition, the last non-missing postbaseline observations prior to or at the time of switch to LY3209590 with a prefilled pen will be summarized and compared to the last non-missing postbaseline observations for insulin glargine by Wilcoxon rank sum test.

# 4.5. Tertiary/Other Endpoints Analysis

#### 4.5.1. Tertiary Efficacy Endpoints

For continuous endpoints, similarly to what is described in section 4.4.2.1 for supportive secondary efficacy endpoints, either ANCOVA model using data from EAS1 or MMRM model using data from EAS2 will be performed.

For the binary outcome endpoints of percentage of participants at Week 52 achieving HbA1c <7%, HbA1c <7% without nocturnal level 2 or 3 hypoglycemia, HbA1c ≤6.5% without level 2 or 3 hypoglycemia, and HbA1c <7% without level 2 or 3 hypoglycemia, EAS1 will be used for the analysis and the details are provided in the table below:

Analysis population	All participants in EAS1 with non-missing baseline measure	
Analysis data	All non-missing observations at Week 52 (Visit 33) during treatment period	
-	regardless of the use of study intervention or rescue therapy	
Endpoint	
 
Binary outcome of HbA1c < 7% with 1 indicating achieving HbA1c target
 
The composite of         
 
binary outcome of HbA1c < 7% at Week 52 with 1 indicating achieving HbA1c target.
 
binary outcome of no nocturnal hypoglycemia (<54 mg/dL or severe) during 52-week treatment period with 1 indicating no occurrence of nocturnal hypoglycemia.
 
 
 
The composite of         
 
binary outcome of HbA1c ≤6.5% at Week 52 with 1 indicating achieving HbA1c target.
 
binary outcome of no hypoglycemia (<54 mg/dL or severe) during 52-week treatment period with 1 indicating no occurrence of hypoglycemia.
 
 
 
The composite of         
 
binary outcome of HbA1c <7% at Week 52 with 1 indicating achieving HbA1c target.
 
binary outcome of HbA1c <7% at Week 52 with 1 indicating achieving HbA1c target.
 
binary outcome of no hypoglycemia (<54 mg/dL or severe) during
 
 
 
	
	52-week treatment period with 1 indicating no occurrence of	
	hypoglycemia.	
Missing data handling	
 
For HbA1c, missing values at Week 52 (Visit 33) will be imputed using the same method for the primary endpoint. The binary outcomes of HbA1c <7% or ≤6.5% will be based on the imputed data.
 
For nocturnal hypoglycemia or hypoglycemia that are included in the composite endpoints, a participant who discontinued the treatment period before Week 52 (Visit 33) is considered as a non-responder (i.e. experienced the event) and the binary outcome value is 0.
 
	
Analysis model	Each endpoint will be analyzed using a logistic regression model including treatment, strata (country, and GLP-1 RA treatment at randomization), and baseline HbA1c value. The odds ratio between LY3209590 and insulin glargine will be used for treatment comparison. The unconditional treatment group effect will be assessed based on a robust variance estimator for g-computation estimators (Ye et al. 2023). Multiple imputation will be performed, and the statistical inference will be based on the multiple imputation framework by Rubin (1987)	

The analysis of fasting serum glucose will be performed for both treatment regimen estimand and efficacy estimand. The analyses of fasting serum glucose by laboratory will use same MMRM model as for the efficacy estimand and same ANCOVA model as for the treatment regimen estimand described in Section 4.4.2.1.

The frequency and proportion of participants who switch to the LY3209590 prefilled pen prior to Week 26 (Visit 25) and Week 52 (Visit 33) will be summarized. A Kaplan-Meier curve will be constructed for the time to switch. Furthermore, the frequency and proportion of participants at each fixed LY3209590 dose level at Week 26 (Visit 25) and Week 52 (Visit 33) will be summarized.

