#### Participants randomly assigned to receive LY3209590

Participants randomly assigned to receive LY3209590 will be on a fixed dose escalation for at least the first 16 weeks of the study. Participants will start LY3209590 on a fixed dose of 100 U per week and will escalate the LY3209590 dose every 4 weeks as required to the set doses of 150, 250, and 400 U per week. Treat-to-target dose adjustments will be based on FBG of 80 to 130 mg/dL (4.4-7.2 mmol/L) and hypoglycemia events (see Section 6.5).

Dose administration will be via a fixed dose autoinjector.

After Week 16, if a participant who has received the fixed dose of 400 U per week for at least 4 weeks has median FBG levels >130 mg/dL, then the investigator should transition the participant to titratable doses using a prefilled pen. This will provide more dosing flexibility and allow dose titrations above 400 U per week.

If a participant transitions from the fixed dose autoinjector to a prefilled pen, they must continue using the prefilled pen for the remainder of the study.

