# 1.1. Objectives, Endpoints, and Estimands

Objectives	Endpoints
Primary	
Demonstrate noninferiority of LY3209590 compared to insulin glargine for the treatment of T2D in adults	Change in HbA1c from baseline to Week 52
Key Secondary (Gated)	
Demonstrate superiority of LY3209590 compared to insulin glargine	Change in HbA1c from baseline to Week 52
Other Secondary	
Compare the effect of LY3209590 to insulin glargine in parameters of glycemic control	
 
Change from baseline to Week 26 for HbA1c
 
Change from baseline to Weeks 16, 26, and 52 for fasting glucose measured by SMBG
 
Insulin dose at Weeks 16, 26, and 52
 

Compare the effect of LY3209590 to insulin glargine on safety endpoints	
 
Incidence and rate of composite of Level 2 and 3 hypoglycemia events during the treatment period
 
Incidence and rate of composite of Level 2 and 3 nocturnal hypoglycemia events during the treatment period
 
Change from baseline to Weeks 26 and 52 in body weight
 

Compare the effect of LY3209590 to insulin glargine on patient-reported outcomes questionnaires	
 
Change from baseline to Weeks 26 and 52 for:
 
TRIM-D, and
 
DTSQ
 
Treatment experience at Weeks 26 and 52 for:
 
DID-EQ, and
 
SIM-Q
 

Tertiary/Exploratory	
Compare the effect of LY3209590 to insulin glargine for efficacy parameters	
 
Percentage of participants at Week 52 achieving:         
 
HbA1c <7%
 
HbA1c <7% without Level 2 or 3 nocturnal hypoglycemia, and
 
HbA1c ≤6.5% without Level 2 or 3 hypoglycemia
 
 
 
Change from baseline to Weeks 26 and 52 for fasting serum glucose
 

Evaluate the percentage of participants receiving LY3209590 that require a transition to the LY3209590 prefilled pen	Percentage of participants that require transition to the LY3209590 prefilled pen at Weeks 26 and 52
Evaluate the percentage of participants at each fixed LY3209590 dose level	Percentage of participants at each fixed dose level at Weeks 26 and 52

Objectives	Endpoints
Compare the effect of LY3209590 to insulin glargine for safety parameters	
 
Incidence and rate of Level 2 hypoglycemia events during treatment period
 
Incidence and rate of Level 3 hypoglycemia events during treatment period
 
Incidence of positive LY3209590 treatment-emergent antidrug antibodies
 

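### The Kaplan-Meier curve for time to pen switch has no stated rule for permanent LY3209590 discontinuation, a competing event; if stoppers are censored, it will sit above the proportion reported beside it

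*SAP*

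**What the plan says.** The tertiary endpoint in SAP 1.1 is "Percentage of participants that require transition to the LY3209590 prefilled pen at Weeks 26 and 52". SAP 4.5.1 summarizes it in two ways. The first is a count and percentage, in a sentence that begins "The frequency and proportion of participants who switch to the LY3209590 prefilled pen prior to Week 26 (Visit 25) and Week 52 (Visit 33) will" and closes by calling for a descriptive summary. The second is the curve: "A Kaplan-Meier curve will be constructed for the time to switch". The section gives no time origin, censoring rule, analysis set or denominator for either.

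Four other provisions bear on the reading:

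- **When a switch can happen.** Protocol 4.1 opens the condition with "After Week 16, if a participant who has received the fixed dose of 400 U per week for at least 4 weeks"; the other half of it is a median fasting glucose above 130 mg/dL. Protocol 6.5.1.1 applies it from Week 16 onward.
- **What follows a permanent stop.** Under Protocol 7.1 and SAP 1.2 the participant stays in the study and attends the remaining visits. Protocol 6.6 ends the supply of study drug.
- **Who must stop.** Protocol 7.1 lists, among other reasons, a participant on 100 U who needs a dose reduction.
- **Default data set.** SAP 4.1 assigns other secondary and tertiary efficacy measures to EAS2. SAP 3 ends EAS2 data at the last LY3209590 dose plus 10 days, or at the start of rescue if earlier. SAP 4.5.1 departs from this default for the HbA1c responder endpoints and for fasting serum glucose, but says nothing about pen switching.

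**The concern.** A participant who has permanently stopped LY3209590 cannot later move to the LY3209590 pen, so stopping is a competing event for switching. Kaplan-Meier with censoring at the stop treats that participant as still able to switch, with the same future risk as those who continue. One minus that curve describes switching in a setting where nobody stops, and only if stopping is unrelated to the need for a higher dose. The endpoint is worded as a percentage of participants, and the proportion printed beside the curve counts what actually happened. Two figures for one endpoint could then appear together, differ, and carry no explanation. At stake is how a reader judges the share of participants for whom four fixed doses are not enough.

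**Working it through.** **The plan's own figure.** The documents give no expected switch rate. The one usable figure is dropout, in the sentence that begins "With the assumption of 15% dropout at Week 52 (Visit 33), approximately 284 participants on LY3209590 and 284 participants on insulin glargine will complete" and goes on to name the full course of treatment. With 670 participants allocated 1:1, 670/2 = 335 per arm, and 335 × 0.85 = 284.75, which agrees with 284. Because that sentence refers to completing treatment, I take dropout as permanent treatment discontinuation.

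**Assumptions not in the documents.** I take a Kaplan-Meier switch probability p of 10% to 40% by Week 52, a constant switch hazard from Week 16 to Week 52, and a constant stop hazard from Week 0.

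**Formulas, with censoring at treatment stop.**

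- Stop hazard: h_d = −ln(0.85)/52 = 0.003125 per week.
- Still on treatment at Week 16: 0.85^(16/52) = 0.951.
- Switch hazard: h_s = −ln(1 − p)/36.
- One minus Kaplan-Meier at week w: 1 − exp(−h_s(w − 16)).
- Cumulative incidence at week w, which is the expected crude proportion of all LY3209590 participants: 0.951 × h_s/(h_s + h_d) × [1 − exp(−(h_s + h_d)(w − 16))].

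**Example, p = 30%, Week 52.** h_s = 0.35667/36 = 0.009908 and h_s + h_d = 0.013033. The cumulative incidence is 0.951 × 0.760 × (1 − e^(−0.4692)) = 0.951 × 0.760 × 0.3745 = 27.1%. The gap is 2.9 points.

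| 1 − KM, Week 52 | Crude, Week 52 | Gap | 1 − KM, Week 26 | Crude, Week 26 | Gap |
|---|---|---|---|---|---|
| 10.0% | 9.0% | 1.0 | 2.9% | 2.7% | 0.2 |
| 20.0% | 18.0% | 2.0 | 6.0% | 5.6% | 0.4 |
| 30.0% | 27.1% | 2.9 | 9.4% | 8.8% | 0.6 |
| 40.0% | 36.2% | 3.8 | 13.2% | 12.4% | 0.8 |

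The Week 52 excess is about 11% in relative terms. Read the other way, crude percentages of 10, 20, 30 and 40 would appear on the curve as 11.1, 22.2, 33.2 and 44.2.

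**Sensitivity to timing and dropout.**

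- *Switches cluster at Week 16.* Only earlier stops matter, so the ratio is 1/0.951 = 1.051. A crude 30% appears as 31.5%, about 5% too high. Over p = 10% to 40% the gap is 0.049p, or 0.5 to 2.0 points, and it is then the same at Week 26.
- *All stops before Week 16.* The crude value is 0.85p and the Week 52 gap is 0.15p, or 1.5 to 6.0 points (0.4 to 2.0 at Week 26).
- *All stops after Week 16.* The Week 52 gap is 0.8 to 2.8 points.
- *Dropout of 10% or 20% instead of 15%.* With the even-rate model, a crude 30% appears as 32.1% or 34.5%.

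**The other reading.** If non-switchers who stop are kept at risk to Week 52, nobody is censored before then. Kaplan-Meier reduces to the crude proportion and the gap is exactly zero. Simulation with 335 participants confirmed this: both summaries averaged 9.1%, 18.0%, 27.1% and 36.1%.

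**Independence of censoring.** Under Protocol 7.1, participants on 100 U who need a reduction leave treatment; they are the least likely to outgrow 400 U. Under the note in Protocol 6.8.3, participants who need nonstudy basal insulin as rescue must first stop study drug; they may be among the more likely to need a higher dose. Both routes tie stopping to dose need, in opposite directions. The curve therefore cannot be relied on for the no-stopping quantity either, and the sign of that error is not determined.

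**The case against.** The strongest reply is that SAP 4.5.1 never says stoppers are censored. A reader might infer that the curve will certainly overstate switching and contradict the proportion. The documents do not support that, because participants who stop stay in the study and carrying them to Week 52 is possible, in which case the discrepancy vanishes. This stands, and the point is conditional for that reason. The EAS2 default favors censoring at about the time of stopping, and no provision says to carry stoppers forward. But that is an inference from a general rule about measurements.

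Second, the efficacy estimand takes a hypothetical view of discontinuation, so a curve for switching if nobody stopped could be intended, and calling it an overstatement presumes the target. This stands in part. The curve would then need that label, and it would still lean on independent censoring, which the stopping rules make doubtful.

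Third, the proportion already answers the endpoint, no test or estimate is taken from the curve, and SAP 4.2 separately plans a figure of time to permanent treatment discontinuation. This stands and limits the importance.

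Fourth, the gaps resemble sampling error: the standard error of a proportion with 335 participants is about 1.6 points at 9% and 2.4 points at 27%. That is true, but both summaries come from the same participants. If stoppers are censored, the mismatch appears in the report whatever the sampling error.

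**Conclusion.** The point holds as a conditional one. The SAP names Kaplan-Meier for an outcome with a competing event and leaves the handling of that event unstated. If stoppers are censored, the curve exceeds the adjacent proportion by roughly 1 to 4 points at Week 52 and under 1 point at Week 26. This assumes 15% dropout at an even rate and 10% to 40% switching at a constant rate from Week 16. Clustering of switches at Week 16 halves the Week 52 gap to about 5% relative. Extreme stop timings give 0.8 to 6.0 points. With non-switchers carried to Week 52 the gap is zero. The switch rate and all timings are assumptions.

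Two stronger readings go too far. One is that the tertiary endpoint itself will be misreported; the crude proportion is planned and answers it, although its denominator should be stated. The other is that this touches the trial's main conclusions. Pen transition is listed as tertiary, the curve is descriptive, and the noninferiority and superiority tests on HbA1c do not use it.

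**What to change.** In SAP 4.5.1, replace the Kaplan-Meier sentence with an Aalen-Johansen cumulative incidence curve for switch to the pen. Measure time from first dose and take permanent discontinuation of LY3209590 as the competing event. Use all treated LY3209590 participants as the denominator for the curve and for the Week 26 and Week 52 proportions. Protocol 7.2 makes withdrawal from the study a permanent discontinuation of treatment as well, so little other censoring should remain before Week 52. Apart from visit windows, curve and proportions should then agree. The same sentence should say whether a switch after the start of rescue counts, because EAS2 also cuts off at rescue while Protocol 6.1.2 keeps those participants on study insulin.

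If the sponsor prefers Kaplan-Meier, the minimum is to state the censoring rule and label the curve as switching in the absence of discontinuation, under independent censoring.

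The cost is one or two SAP sentences and a standard software option. It needs no new data and no change to any test: a free improvement.
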